6.3 Distinction Between Research Protocol and Clinical Standard of Care

It is important to emphasize that patients enrolled in this study will undergo the same clinically indicated ablation procedure and receive the same standard of care as non-participating patients. The sole distinction for research participants is the inclusion of the two additional mapping sequences: one performed prior to ablation (for the paired voltage amplitude comparison) and one performed after ablation (for the comparative conduction block assessment). Furthermore, all mapping and ablation technologies utilized during these additional research steps, including the Optrell and Octaray catheters, as well as their respective 3D mapping systems and software, are

fully approved for clinical use by the FDA, CE, and AMAR, and are routinely employed in standard clinical practice at our institution.

7. FOLLOW-UP

7.1 Acute Safety Follow-Up

Because the investigational component of this study consists solely of additional electrophysiological mapping time using commercially approved technologies within a standard-of-care procedure, an independent Data Safety Monitoring Board (DSMB) will not be established. Instead, a designated Medical Monitor will oversee safety reporting throughout the study.

The Medical Monitor will be a senior cardiologist with expertise in cardiac procedures who is not involved in the conduct of the study and has no direct role in patient enrollment, procedures, or data analysis. The Medical Monitor will independently review all reported safety events.

All acute procedural complications and safety events will be reviewed by the Medical Monitor within 72 hours of notification.

Adverse Event (AE) and Serious Adverse Event (SAE) forms will be completed by the research coordinator in collaboration with the procedural operator and documented in the study Case Report Form (CRF; Appendix C).

If serious adverse events directly attributable to the repolarization mapping protocol occur in ≥ 2 of the first 10 enrolled patients, study enrollment will be temporarily paused, and an ad-hoc safety review will be conducted by the Medical Monitor and study leadership to determine whether protocol modification or study termination is necessary.

Definitions

AE

An AE is any unfavorable and unintended medical occurrence in a study participant undergoing the procedure, whether or not it is considered related to the study protocol.

CONFIDENTIAL

166 **SAE**

167 An SAE is any adverse event that results in one or more of the following outcomes:

- 168 • Death
- 169 • Life-threatening event
- 170 • Stroke/TIA
- 171 • Persistent or significant disability or incapacity
- 172 • Unplanned hospitalization or prolongation of hospitalization
- 173 • Any important medical event that may jeopardize the patient or require medical or surgical
- 174 intervention to prevent one of the outcomes listed above

175
176 For the purposes of this study, the following procedural complications will be classified and
177 reported as SAEs:

- 178 • Pericardial effusion or cardiac tamponade
- 179 • Stroke/TIA
- 180 • Phrenic nerve injury
- 181 • Vascular access complications requiring intervention
- 182 • Esophageal injury
- 183 • Heart failure exacerbation requiring treatment
- 184 • Prolonged hospitalization (>24 hours beyond the expected post-procedural course)
- 185 • Any other serious adverse event related to the procedure

186

187 **Safety Follow-Up Period**

188 Formal protocol-mandated safety follow-up will extend through 7 days after the procedure or until
189 hospital discharge, whichever occurs later.

190 All AEs and SAEs occurring during this period will be documented in the CRF and reviewed by
191 the Medical Monitor.

192

193 **7.2 Clinical Follow-Up and Rhythm Monitoring**

194 Patients will undergo highly structured longitudinal follow-up to monitor for clinical and
195 subclinical arrhythmia recurrence and symptom status.

196 **Clinic Visits:**

CONFIDENTIAL

Patients will be evaluated at the following time points after the ablation procedure:

- 1 month \pm 14 days
- 3 months \pm 30 days
- 6 months \pm 30 days
- 9 months \pm 30 days
- 12 months \pm 30 days

Visits at 3 and 12 months will be conducted in person, while other visits may be conducted in person or via telemedicine, depending on clinical circumstances.

During these visits, the following information will be collected:

- Symptoms suggestive of arrhythmia recurrence
- Medication use, including antiarrhythmic drugs and anticoagulation
- Interval hospitalizations or cardiovascular events
- Standard ECG documentation when available

Rhythm Monitoring:

To systematically detect symptomatic and asymptomatic arrhythmia recurrence, patients will undergo scheduled ambulatory rhythm monitoring during follow-up.

A minimum of three 48-hour Holter monitors will be performed at:

- 3 months \pm 30 days
- 6 months \pm 30 days
- 12 months \pm 30 days

Additional rhythm monitoring (Holter, event monitor, or ECG) may be performed at the treating physician's discretion if symptoms suggest arrhythmia recurrence.

Recurrence of atrial arrhythmia will be defined as documented AF or atrial tachycardia lasting \geq 30 seconds after the standard 2-month blanking period.

Community-Based Testing: To facilitate protocol compliance, both the 12-lead ECGs and the 24-hour Holter monitors may be performed locally at the patient's primary care clinic (Kupat Holim). The study coordinator is responsible for retrieving and analyzing these community-based reports and logging the data into the study database.

228

229 **7.3 Post-Procedure Antiarrhythmic Drug Management**

230 The use of AADs following the ablation procedure will be at the discretion of the treating
231 electrophysiologist and managing physician, in accordance with routine clinical practice.

232 Continuation, initiation, or discontinuation of AAD therapy during follow-up will not be dictated
233 by the study protocol. All AAD use will be prospectively documented, including drug type, dosing,
234 changes, discontinuation, and replacement. This information will be incorporated into the clinical
235 database and considered in exploratory analyses of arrhythmia recurrence.

236

237 **7.4 Redo Procedures and Lesion Durability Assessment**

238 Any documented recurrence of atrial flutter or AF will prompt consideration for a redo procedure,
239 as clinically indicated.

240 If a redo procedure is performed during the 12-month follow-up period, the index protocol
241 performed again: a left atrial 3D map using TPI with left atrial voltage mapping will be performed
242 using the Octaray catheter. The Octaray catheter will then be exchanged for the Optrell catheter,
243 and a second high-density voltage map will be acquired on the same 3D map (remap). A high
244 density Multipolar map using parallel mapping will be performed in the same time with the Optrell
245 catheter. All the maps need to have a fill threshold ≤ 3 mm to allow sufficient density. For patient
246 in atrial fibrillation, an electrical cardioversion will be performed and mapping will be performed
247 during coronary sinus pacing. For patient in sinus rhythm, mapping will be performed during
248 coronary sinus pacing. For patient in atrial flutter, mapping will be performed in arrhythmia.

249 • **Block Assessment:** Prior to delivering any new ablation, the operator must re-assess
250 conduction block across all linear ablation lesions created during the index procedure.

251 **Gold Standard Block Assessment:** Creation of a full activation map using the Octaray catheter
252 (often requiring pacing maneuvers) to establish the gold-standard confirmation of block. Time to
253 determination, from the beginning of the mapping to block confirmation, and the binary result will
254 be recorded.

255 **Optrell Vector Assessment:** Real-time evaluation of conduction vectors using the Optrell catheter
256 and V8 software. The time to determination, from the beginning of the mapping (pacing start) to
257 block confirmation, and the binary result (block vs. no block) will be recorded.

• **Data Capture:** The presence or absence of durable conduction block across each previously ablated line, as determined by the standard activation map, must be meticulously documented in a dedicated "Redo Procedure" module within the Case Report Form (CRF).

• **Treatment:** Subsequent ablation of any identified gaps or new arrhythmogenic substrates will be performed according to the operator's clinical discretion and standard of care.

For every redo procedure, a complete Redo Procedural CRF (Appendix F) will be filled.

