4.2 Secondary Endpoints

- **Bipolar Voltage Correlation:** Statistical correlation and evaluation of systematic bias (limits of agreement) between the bipolar voltage amplitudes recorded by the two catheters in matched anatomical regions.
- **Multipolar Voltage Correlation:** Statistical correlation and evaluation of systematic bias (limits of agreement) between the multipolar voltage amplitudes recorded by the Optrell catheter and the bipolar voltage amplitudes recorded by the Octaray catheter in matched anatomical regions
- **Clinical Efficacy:** Freedom from any documented atrial tachyarrhythmia lasting ≥ 30 seconds at 1, 3, 6, 9, and 12 months.
- **Safety:** Incidence of acute procedural complications prior to hospital discharge.

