10. STUDY GOVERNANCE AND SAFETY OVERSIGHT

An independent Data Safety Monitoring Board will not be established for this investigator-initiated observational study due to the limited sample size and the fact that the investigational component consists solely of additional electrophysiological mapping using commercially approved technologies within a standard-of-care ablation procedure.

Safety oversight will be performed by a designated Medical Monitor, who will review all reported acute procedural complications (e.g., cardiac tamponade, stroke or transient ischemic attack, and vascular complications requiring intervention) within 72 hours of occurrence.

If two or more unexpected severe adverse events potentially attributable to the repolarization mapping protocol occur within the first ten enrolled patients, study enrollment will be temporarily paused and an ad-hoc safety review will be conducted to determine whether protocol modifications are required before enrollment resumes.

Safety events and protocol adherence will be monitored throughout the study.

Study Registration: the study will be registered in a public clinical trials registry (e.g., ClinicalTrials.gov) prior to enrollment of the first patient, in accordance with International Committee of Medical Journal Editors (ICMJE) requirements.

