12. APPENDIX A - STUDY FLOWCHART

13. APPENDIX B- Schedule of Assessments

Study Activity	Screening / Pre- Procedure	Procedure Day	Post-Procedure / Discharge	1 Month	3 Months	6 Months	9 Months	12 Months
Informed consent	-----X-----							
Eligibility confirmation	X	X						
Demographics and medical history	X							
Arrhythmia Classification (PAF / PerAF / Flutter)	X							
Baseline medications	X		X	X	X	X	X	X
Standard Ablation according to protocol		X						
Procedural safety assessment		X	X					
Adverse event assessment			X	X	X	X	X	X
ECG			X	X	X	X	X	X
AAD documentation			X	X	X	X	X	X
48-hour Holter					X	X		X
Arrhythmia recurrence assessment				X	X	X	X	X
Documentation of redo ablation (if applicable)					X	X	X	X

14. Appendix C – AE / SAE Form

Field	Description / Options
Study ID	
Hospital MRN	
Event number	
Event classification	 AE  SAE
SAE Category	
SAE type	 Pericardial effusion / tamponade  Stroke / TIA  Vascular complication requiring intervention  Phrenic nerve injury  Esophageal injury  Heart failure exacerbation requiring treatment  Prolonged hospitalization (>24h)  Other (specify)
Event description	
Date of onset	
Date of resolution	
Severity	 Mild  Moderate  Severe
Seriousness criteria	 Death  Life-threatening event  Prolonged hospitalization  Persistent disability  Medically significant event
Relationship to procedure	 Related to procedure  Possibly related to study mapping protocol  Unrelated
Action taken	 Observation  Medication  Intervention  Hospitalization  Other
Outcome	 Resolved  Ongoing  Resolved with sequelae  Death
Reported to Medical Mon	 Yes  No
Date reported	
Investigator signature	

15. Appendix D – Procedural CRF**SECTION 1: DEMOGRAPHICS AND CLINICAL HISTORY/DATA**

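### The protocol's only numerical enrolment-pause trigger is given in two conflicting versions (Sections 7.1 and 10), and the adverse event form does not fully support either

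*Protocol*

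**What the plan says.** Section 7.1 declines a DSMB, appoints a Medical Monitor, and sets a pause rule for "serious adverse events directly attributable to the repolarization mapping protocol" that "occur in ≥ 2 of the first 10 enrolled patients". The review that follows may lead to protocol modification or study termination.

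Section 10 sets the rule again in other terms: "If two or more unexpected severe adverse events potentially attributable to the repolarization mapping protocol occur within the first ten enrolled patients". The review it describes decides whether modifications are needed before enrolment resumes. Termination is not mentioned.

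The Medical Monitor's review is due "within 72 hours of notification" in Section 7.1 and "within 72 hours of occurrence" in Section 10.

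The AE/SAE form in Appendix C records AE or SAE class, severity (mild, moderate, severe), seriousness criteria and a relationship field with three options: related to the procedure, "Possibly related to study mapping protocol", and unrelated.

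Section 6.2 describes voltage, multipolar, activation and vector mapping. Section 6.3 says that research participation adds two mapping sequences, one before and one after ablation. Section 9.2 lists tamponade, stroke or TIA, vascular complications and phrenic nerve injury among the risks inherent to catheter ablation. Section 8.1 targets 30 patients.

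**The concern.** No other numerical safety trigger appears in the protocol, and it applies to the first third of the cohort (10 of 30). Its two statements differ in event class, attribution level, counting unit and expectedness. If those differences can change the decision, whoever applies the rule must choose a version after the events are known. That is what a pre-specified trigger is meant to prevent.

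Three further points make the rule harder to apply. The mapping it names does not match any mapping in the protocol. One of its terms, *unexpected*, has no definition. The form that should supply the inputs lacks one term from each version. The primary endpoints and their analyses are not affected; what is at stake is whether the safety decision is reproducible.

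**Working it through.** **No plan figure to reproduce.** The protocol states no event rate, error probability or operating characteristic for the rule. The main check is therefore a comparison of the texts.

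| Element | Section 7.1 | Section 10 | Appendix C field |
|---|---|---|---|
| Event class | serious | severe | both recorded, separately |
| Expectedness | no condition | unexpected only | none |
| Attribution | directly | potentially | *possibly related* only |
| Counting unit | patients (at least 2 of 10) | events (two or more) | event-level form |
| Stated outcome of review | modification or termination | modification | – |
| 72-hour review starts at | notification | occurrence | dates of onset and of report |

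**Does the difference change the decision?** Two cases show that it can, in both directions.

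1. Two of the first ten patients each have a mild pericardial effusion judged directly due to the added mapping. Section 7.1 classifies pericardial effusion as an SAE, so its trigger is met. Section 10's is not, because the events are not severe.
2. One patient has two unexpected severe events that are potentially due to the mapping. Section 10's trigger is met. Section 7.1's is not, because only one patient is affected.

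Neither rule contains the other, so adopting the stricter one is not an available default.

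**Can the form feed the rule?** Partly. For Section 7.1 it supplies SAE class but no level for direct attribution to mapping. For Section 10 it supplies severity and a near match to *potentially attributable*, but nothing on expectedness.

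**The 72-hour clock.** If an event is reported more than 72 hours after it happens, Section 10's deadline has passed before Section 7.1's clock starts.

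**Illustrative size (assumed rates).** Let X be the number of the first 10 patients with a qualifying event, independent with probability p. Then P(X ≥ 2) = 1 − (1 − p)^10 − 10p(1 − p)^9.

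- p = 0.02: 1 − 0.8171 − 0.1667 = 0.016
- p = 0.05: 1 − 0.5987 − 0.3151 = 0.086
- p = 0.10: 1 − 0.3487 − 0.3874 = 0.264
- p = 0.20: 1 − 0.1074 − 0.2684 = 0.624

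*Attribution word alone.* Suppose half of the patients with a potentially attributable event have a directly attributable one (assumption), all else equal. At a potential rate of 10%, the pause probability is 0.264 under *potentially* and 0.086 under *directly*. At 20% it is 0.624 against 0.264. At 2% it is 0.016 against 0.004 (p = 0.01: 1 − 0.9044 − 0.0914).

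*Counting unit alone.* Let f be the share of affected patients with two or more events. The probability by events is P(X ≥ 2) + f·P(X = 1). At p = 0.10 this is 0.264 + 0.1 × 0.387 = 0.303 for f = 0.1, and 0.264 + 0.3 × 0.387 = 0.380 for f = 0.3.

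The attribution word and the counting unit both raise Section 10's probability relative to Section 7.1's. The *unexpected* and *severe* filters lower it. The net direction cannot be determined from the protocol.

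**The case against.** The best defence is that the rule is untidy but usable. Section 7.1 says that the investigational component is additional mapping time, Section 6.3 defines it, and Appendix C refers to the study's mapping protocol, so the misnamed mapping has only one plausible referent. Neither section says that a pause occurs *only* under its own condition, so both triggers could run side by side. The Medical Monitor reviews every reported event and is not confined to the tick-boxes. Much of this stands, and it rules out several stronger readings:

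- **That the rule cannot be applied, or can never fire, because no repolarization mapping is done.** This ignores the evident referent. It is a wording error repeated in two sentences.
- **That Section 10 would never count tamponade, stroke or vascular complications.** The protocol does not define *unexpected* and does not say that the Section 9.2 list is excluded. That list is open-ended, and Section 7.1 names SAEs that are not on it (esophageal injury, heart failure exacerbation). It is unclear whether the listed complications count; exclusion is not established.
- **That Section 10 rules out termination.** It does not mention termination, but it does not exclude it either.
- **That the safety endpoint contradicts the safety follow-up.** Section 4.2 defines the endpoint as "Incidence of acute procedural complications prior to hospital discharge", and the procedural CRF's complications section is likewise completed at discharge. Section 7.1's longer window ("Formal protocol-mandated safety follow-up will extend through 7 days after the procedure or until" discharge, whichever is later) governs collection and review. An endpoint narrower than its collection window is a choice, not a contradiction.

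The defence does not remove the conflict itself. The protocol nowhere says that either trigger suffices. Even if it did, direct attribution and expectedness would still have to be judged without a recorded field.

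**Conclusion.** The point holds as an internal contradiction in a safety decision rule. Sections 7.1 and 10 set different triggers for the same pause, neither is uniformly stricter, and identifiable sets of events give opposite answers. The wrong mapping name, the undefined *unexpected*, the partial gap in Appendix C and the two starts of the 72-hour clock add to it.

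The contradiction rests on the text alone and needs no assumption. Its size does. With assumed per-patient rates of 10% to 20%, and half of potentially attributable cases being directly attributable, the attribution word moves the pause probability by about 18 to 36 percentage points (0.264 − 0.086 and 0.624 − 0.264). At 2% the shift is about 1 point. The numerical effect is therefore material only if event rates are not low.

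**What to change.** Before the first patient is enrolled, the sponsor should:

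- reconcile Sections 7.1 and 10 into one pause rule, stated once and cross-referenced, with one event class, one attribution level, one counting unit and one stated consequence;
- replace the reference to repolarization mapping with the added mapping of Sections 6.2 and 6.3;
- define *unexpected* if the term is kept, saying how it relates to the Section 9.2 risks, and add an expectedness field to Appendix C;
- make the Appendix C relationship options match the attribution term chosen;
- give the Medical Monitor's 72-hour review one starting point.

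Which trigger and which clock are right is for the sponsor to decide. The cost is protocol wording and minor changes to the AE/SAE form. The procedures, sample size and endpoints do not change.

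### Sections 7.1 and 10 give two different triggers for the same early enrolment pause, and the protocol does not say which governs or that either is enough

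*Protocol*

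**What the plan says.** Section 7.1 of the protocol pauses enrolment temporarily if "serious adverse events directly attributable to the repolarization mapping protocol occur in ≥ 2 of the first 10 enrolled patients". An ad-hoc review by the Medical Monitor and study leadership follows, "to determine whether protocol modification or study termination is necessary". Safety events are to be "reviewed by the Medical Monitor within 72 hours of notification".

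Section 10 pauses enrolment temporarily if "two or more unexpected severe adverse events potentially attributable to the repolarization mapping protocol occur within the first ten enrolled patients". Its ad-hoc review is "to determine whether protocol modifications are required before enrollment resumes", and it sets the Medical Monitor's review of acute complications "within 72 hours of occurrence".

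Section 7.1 makes the form in Appendix C the record for AEs and SAEs. On that form the only relationship option that names mapping is "Possibly related to study mapping protocol"; the other two are relation to the procedure and no relation. Severity (mild, moderate, severe) is one field and "Seriousness criteria" is another. There is no field for expectedness.

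**The concern.** Both sections describe the same action over the same window, so a reader expects one rule. The study has no DSMB, this is its only pre-set safety trigger, and it covers the first 10 of the 30 planned patients. Safety of dual-catheter mapping is also a stated secondary objective. If two events in the first ten patients meet one wording and not the other, one section of the protocol orders a pause and the other does not. The decision would then be argued after the events are known, which a pre-set trigger is meant to prevent.

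**Working it through.** The protocol gives no operating characteristic for the trigger, so there is no figure to reproduce. The check is mainly a comparison of text.

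**1. The two rules side by side**

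| Element | Section 7.1 | Section 10 |
|---|---|---|
| Type of event | serious | unexpected and severe |
| Attribution | direct | potential |
| Counting unit | patients (at least 2) | events (at least 2) |
| Window | first 10 enrolled | first 10 enrolled |
| Named outcome of the review | modification or termination | modification before restart |
| 72-hour review runs from | notification | occurrence |

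**2. Does one rule contain the other?** Section 10 is looser on attribution and on counting unit, but narrower because it requires the events to be unexpected. *Serious* and *severe* are also separate items: 7.1 defines an SAE by outcome, and Appendix C records severity apart from seriousness. Two cases show that neither rule contains the other.

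- Case A: two patients each have a tamponade caused directly by mapping. Section 7.1 is met. Section 10 may not be, because 9.2 already lists tamponade as a risk, so it can be called expected.
- Case B: one patient has two unexpected severe events potentially due to mapping. Section 10 is met. Section 7.1 is not, because only one patient is affected.

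**3. Can the terms be applied?** *Unexpected* is not defined. *Repolarization* mapping appears only in these two rules and matches no procedure in 6.2, which describes voltage, vector and activation mapping. For 7.1, Appendix C supplies SAE status and patient ID but no option for direct attribution to mapping; relation to the procedure does not separate mapping from ablation. For section 10, it supplies the severity grade and possible relation to mapping but not expectedness. Each rule is therefore mostly captured, with one element missing.

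**4. The review clock.** If notification comes *d* hours after the event, the 7.1 deadline falls *d* + 72 hours after the event and the section 10 deadline falls at 72 hours. Section 7.1 gives no time limit for notifying the Medical Monitor, so *d* is not bounded.

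**5. Illustration of the counting unit alone.** The protocol gives no SAE rate, so all rates here are assumed. Let *p* be the chance that a patient has a qualifying event, and *q* the chance that a single affected patient has two or more. Hold the type of event and the attribution the same in both rules.

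- Counting patients: P = 1 − (1−p)^10 − 10p(1−p)^9
- Counting events: the same plus 10p(1−p)^9 × q

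For p = 0.05, the first is 1 − 0.5987 − 0.3151 = 0.086. With q = 0.10 the second adds 0.0315, giving 0.118; with q = 0.25 it adds 0.0788, giving 0.165.

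| p (assumed) | Counting patients | Counting events, q = 0.10 to 0.25 (assumed) |
|---|---|---|
| 2% | 1.6% | 3.3% to 5.8% |
| 5% | 8.6% | 11.8% to 16.5% |
| 10% | 26.4% | 30.3% to 36.1% |

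This shows only that the unit matters. It does not predict how often the rules would part in this study.

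**The case against.** The best defence is that each section states a sufficient condition. Both say that enrolment pauses if something happens; neither says only if. Read together, meeting either one requires a pause. The clocks can be reconciled as well, since a review within 72 hours of the event is also within 72 hours of notification, and section 10 does not forbid termination. The Medical Monitor is outside the conduct of the study, reviews every reported event, and can judge directness and expectedness without a tick-box. *Repolarization* can be taken as a slip, because Appendix C speaks simply of the study mapping protocol.

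Much of this stands, and it limits the point. A reader might infer that nobody could tell whether to pause. That goes too far, because the either-rule reading is available and sensible. The protocol does not state it, however, and a team holding only one section would reasonably apply only that section.

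A reader might also infer that neither rule can be applied from the AE form. The documents do not support that: the form holds most elements, one is missing from each rule, and nothing says that the decision must rest on the form alone.

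Nor can it be said that the word *unexpected* removes a fixed share of the named complications. The risk list in 9.2 is expressly open-ended and describes the risks of ablation, which need not be what is expected from added mapping.

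**Conclusion.** The protocol contradicts itself on the threshold of its only pre-set safety trigger. Three terms of the trigger differ, neither rule contains the other, and no text says which governs or that either suffices. The review clock and the named outcomes differ as well. The conclusion rests on the wording alone. Case A further assumes that a complication listed in 9.2 may be called expected, which the protocol leaves open.

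The consequence is bounded. All AEs and SAEs in the safety period are still recorded and reviewed by the Medical Monitor, and no endpoint or analysis depends on the rule. A reader should not infer that events would be missed. What is at stake is whether two qualifying events lead to a pause by rule or by argument. The point is worth correcting before enrolment because the correction is a matter of wording.

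**What to change.** State one rule in 7.1 and have section 10 only refer to it. Suggested text:

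> Enrolment pauses if two or more AEs that are serious (7.1 definition) or graded severe, and judged at least possibly related to the study mapping protocol (Appendix C), occur within the first 10 enrolled patients; the Medical Monitor and study leadership then decide on modification or termination.

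Drop *unexpected*, *directly* and *repolarization*, and use one 72-hour clock in both places.

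This rule covers every case that triggers either current rule. Case A qualifies because the events are serious and at least possibly related. Case B qualifies because the events are graded severe and events are counted. An event due directly to mapping is at least possibly related, so it belongs under the existing mapping option on the form. No new data item is needed.

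The cost is a text change in two sections and a temporary pause that may trigger somewhat more often than under either rule alone. As an illustration with assumed rates, if the wider rule doubled the share of patients with a qualifying event from 5% to 10%, the chance of at least two affected patients in ten would rise from 8.6% to 26.4%. Counting events adds a little more. A pause leads to a review and does not in itself end the study.

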8. STATISTICAL CONSIDERATIONS

8.1 Sample Size

A sample size of 30 patients is targeted. Because each patient will likely contribute multiple mapped regions and ablation lines (e.g., roof line, posterior wall, CTI), this will yield a robust number of paired observations for both voltage and block concordance analyses.

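### The only written pause rule covers the first 10 of 30 patients; in patients 11 to 30 no event count obliges a pause or ad-hoc review

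*Protocol*

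**What the plan says.** Section 7.1 of the protocol declines a DSMB and states that "a designated Medical Monitor will oversee safety reporting throughout the study". It adds that "All acute procedural complications and safety events will be reviewed by the Medical Monitor within 72 hours of notification". Its pause rule begins "If serious adverse events directly attributable to the repolarization mapping protocol occur in ≥ 2 of the first 10 enrolled patients"; the consequence ("of the first 10 enrolled patients, study enrollment will be temporarily paused") is a temporary halt to enrolment and an ad-hoc review by the Medical Monitor and study leadership.

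Section 10 restates the rule with different terms: "If two or more unexpected severe adverse events potentially attributable to the repolarization mapping protocol occur within the first ten enrolled patients", again followed by a pause and an ad-hoc review. The same section says in general terms: "Safety events and protocol adherence will be monitored throughout the study".

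Section 8.1: "A sample size of 30 patients is targeted".

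Section 7.4 repeats the study mapping at later procedures: "If a redo procedure is performed during the 12-month follow-up period, the index protocol" is carried out again. Neither version of the rule mentions redo procedures.

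**The concern.** The patients outside the rule undergo the same dual-catheter mapping as those inside it. The protocol gives no reason, such as a learning period, for watching only the first 10. It describes both catheters as approved and in routine use at the institution (sections 2.4 and 6.3). If two affected patients in 10 justify a pause in patients 1 to 10, the same count in patients 11 to 20 should at least compel the same review.

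As written it does not. One affected patient at position 10 and one at position 11 meet no trigger, nor would five among patients 11 to 20. From patient 11 the protocol requires each event to be reviewed, but it names no count that leads to action and no criterion for a pause. What is at stake is a predictable response to a cluster of mapping-related serious events in two thirds of the cohort, in a study without a DSMB.

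**Working it through.** **Plan's own figure.** None. The protocol states no assumed event rate and no operating characteristics for the rule, so there is nothing to reproduce.

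**Inputs.**
- Threshold: 2 or more affected patients among the first 10 enrolled (section 7.1).
- Planned size: 30 (section 8.1). Outside the rule: 30 − 10 = 20 patients, 20/30 = 67%.
- Per-patient rate *p* of mapping-attributable serious events: not in the documents. Assumed values are 1%, 2%, 5%, 10% and 20%, with patients independent.

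**Formulas.**
- A, rule as written fires: 1 − (1−p)^10 − 10p(1−p)^9.
- B, two or more affected among patients 11 to 30: 1 − (1−p)^20 − 20p(1−p)^19.
- C, rule never fires and two or more are affected among patients 11 to 30: (1 − A) × B.
- D, the same threshold over any 10 consecutive patients of 30: 200,000 simulated studies.

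**Example at p = 10%.** A = 1 − 0.3487 − 0.3874 = 0.264. B = 1 − 0.1216 − 0.2702 = 0.608. C = 0.736 × 0.608 = 0.448.

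| Assumed p | A | B | C | D |
|---|---|---|---|---|
| 1% | 0.4% | 1.7% | 1.7% | 2.1% |
| 2% | 1.6% | 6.0% | 5.9% | 7.3% |
| 5% | 8.6% | 26.4% | 24.1% | 31.4% |
| 10% | 26.4% | 60.8% | 44.8% | 69.3% |
| 20% | 62.4% | 93.1% | 35.0% | 97.0% |

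**Check on D.** Three separate blocks of 10 give 1 − (1 − A)^3, which must be below D because the rolling window contains those blocks. The results are 1.3%, 4.8%, 23.7%, 60.1% and 94.7%, each below D as expected.

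**Limits of the model.** The figures describe the section 7.1 rule, which counts patients. Section 10 counts events, so two events in one patient could meet it. Redo exposures are not in the model.

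**Redo procedures, from the text.** Section 7.1 counts events in the first 10 enrolled patients, with no time limit and no restriction to the index procedure. A mapping-attributable event at a redo in patients 1 to 10 therefore counts; the same event in patients 11 to 30 does not.

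**The case against.** The strongest reply has four parts.

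1. *Oversight does not end at patient 10.* This is correct. The Medical Monitor is independent of the study's conduct and reviews every safety event throughout, and nothing bars a discretionary pause. A reader might infer that no number of events could pause the study after patient 10. The documents do not support that; they show only that no written rule would require it.

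2. *Redo mapping is not excluded.* This is also correct for patients 1 to 10. A reader might infer that the rule ignores redo mapping, or that nearly all redo exposures fall after it has lapsed. The rule has no time limit, and if redo rates were similar across patients about one third (10/30) of redo exposures would be in the first 10. Nor does an enrolled patient who is still waiting for mapping lose a place: that patient stays in the count, and only one who is never mapped takes up a place for nothing.

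3. *An early check is a legitimate choice in a 30-patient observational study of approved devices, and the Medical Monitor, not the pause rule, is what replaces the DSMB.* That is fair. It makes this a gap in the safety plan and not a contradiction. It does not explain why the threshold should stop at 10 when the exposure does not change.

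4. *The rates are assumptions, and the rolling rule fires more often largely because it watches three times as many patients.* Both statements are true. At 1% the two rules fire in 0.4% and 2.1% of studies, so the gap seldom matters if the hazard is very low. The wider coverage is, however, the purpose of the change.

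**Conclusion.** The point holds in this form: for patients 11 to 30 no count of mapping-attributable serious events obliges a pause or an ad-hoc review, no criterion is attached to the Medical Monitor's continuing review, and redo mapping is not explicitly addressed. That 20 of 30 patients fall outside the rule is certain from the text.

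The practical size depends on a rate the documents do not give. At an assumed 10%, the rule as written is met in about a quarter of studies, and in 45% of studies two or more patients among 11 to 30 would be affected without the trigger ever being met. At 2% that last figure is 5.9%. These figures rest on independent patients, a constant rate and the section 7.1 definition.

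**What to change.** Keep the sponsor's threshold and consequence (two or more affected patients in 10 leads to a pause and an ad-hoc review), and amend the rule as follows:

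- Apply it to any 10 consecutive patients who underwent the study mapping, through the last patient.
- Count a mapping-attributable serious event at a redo against the place that patient took in the sequence at the index procedure.
- State that once enrolment is complete, when a pause has no effect, meeting the threshold still prompts the ad-hoc review, which also considers whether research mapping at redo procedures continues.
- Use one wording in sections 7.1 and 10. At present they differ on serious versus unexpected severe, direct versus potential attribution, patients versus events, and whether termination is a possible outcome. Both refer to repolarization mapping, which the protocol does not describe elsewhere. The sponsor needs to reconcile these terms.

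The cost is a short amendment in two sections and a running tally kept by the coordinator. If the true rate is 2%, the trigger would be met in about 7% of studies instead of about 2%, and slightly more once redo events are counted, because the simulation contains none.
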